4.3. Eligibility Criteria for the Extension Treatment Period

Inclusion Criteria:

1. Completion of the Week 24 study visit (including EGD) including subjects who discontinued study treatment due to lack of clinical efficacy and started rescue therapy between Weeks 16 and 24. Rescue therapy must be discontinued on the day etrasimod is initiated in the Extension Treatment Period.
2. Compliance with study procedures during the Double-Blind Treatment Period as assessed by the Investigator
3. No notable safety concerns during the Double-Blind Treatment Period, as determined by the Investigator
4. Willing to comply with all study visits and procedures for the Extension Treatment Period

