Efficacy Evaluable Set; (Extension Treatment Period)	The Efficacy Evaluable Set will include subjects who receive at least one dose of etrasimod and have at least one efficacy measurement in the Extension Treatment Period (endpoint specific)

Baseline for the Extension Treatment Period is defined as the last measurement prior to the first etrasimod dose started at Week 24.

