1. INTRODUCTION

This Statistical Analysis Plan (SAP) describes the statistical rationale, methods, rules, and conventions to be used in the presentation and analysis of efficacy, safety, pharmacokinetic (PK), CCI [REDACTED] for Clinical Study Protocol APD334-206. It describes the data to be summarized and analyzed, including specifics of the statistical analyses to be performed (ICH 1998). This SAP is based on the Clinical Study Protocol APD334-206 Amendment 3.0, dated XX January 2023 and will cover the whole study period (i.e., Double-Blind Treatment Period and Extension Treatment Period). CCI [REDACTED]
[REDACTED]

The table, figure, and listing (TFL) shells are prepared in a separate file based on this analysis plan. Upon approval of the SAP, some updates (including, but not limited to titles, footnotes, headings and re-numbering of tables) on TFL shells are allowed without SAP amendment if the updates within TFL shells do not conflict with the contents of the SAP.

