2.4. ESTIMANDS

The primary and secondary estimands to support regulatory decisions are described in Table 1 below. Supplementary analyses for the primary and secondary estimands will be performed in the Modified Full Analysis Set (mFAS), Completers, and Per Protocol Set, respectively.

List of Estimands

Estimand	Definition	Attributes			
		Population	Variable/ Endpoint	Intercurrent event handling strategy	Population-level summary measure
Primary Estimand	Efficacy of etrasimod on esophageal peak eosinophil count (PEC) at Week 16	Full Analysis Set	Percentage change from Baseline in esophageal PEC at Week 16	Subjects with missing data for any reason (including early discontinuation) or who initiated rescue medication and/or rescue procedure before the primary efficacy assessments prior to Week 16 will have subsequent PEC data set to missing from that point forward through Week 24. The missing data at Week 16 will be imputed using a multiple imputation (MI) method.	Differences between etrasimod (2 mg, 1 mg and any dose) and placebo in percent change from Baseline in esophageal PEC at Week 16

Key Secondary Estimand 1	Efficacy of etrasimod on Dysphagia Symptom Questionnaire (DSQ) at Week 16	Full Analysis Set	Change from Baseline in DSQ at Week 16	Same as the intercurrent event handling strategy for the primary estimand	Differences between etrasimod (2 mg, 1 mg and any dose) and placebo in change from Baseline in DSQ at Week 16
Key Secondary Estimand 2	Efficacy of etrasimod on esophageal PEC at Week 16	Full Analysis Set	Change from Baseline in esophageal PEC at Week 16	Same as the intercurrent event handling strategy for the primary estimand	Difference between etrasimod (2 mg, 1 mg and any dose) and placebo in change from Baseline in esophageal PEC at Week 16
Key Secondary Estimand 3	Efficacy of etrasimod on esophageal PEC at Week 16	Full Analysis Set	Proportion of subjects with esophageal PEC < 15 eos/hpf at Week 16	Subjects in any of the following cases will be treated as nonresponders: use of rescue medication and/or rescue procedure prior to Week 16; premature discontinuation for study due to any reason prior to Week 16; or with missing data at Week 16 for any reason. If subject had rescue medication and/or rescue procedure after Week 16, any assessment after the rescue medication and/or rescue procedure time will be set to missing.	Difference between etrasimod (2 mg, 1 mg and any dose) and placebo in the proportion of responders at Week 16

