8.3. MISSING DATA

Missing adverse event (AE) relationship to study drug and AE seriousness will be imputed as described in Section 17.1.1.2 and 17.1.3, respectively. Partial or missing AE start dates, Concomitant Medication (CM) start dates, and hospitalization dates will also be imputed as described in Appendix 2. No other missing safety data will be imputed.

Missing efficacy data will be handled as described in Sections 16.1.2, 16.2.2, and 16.3.2. In the primary analysis of the primary endpoint, PEC after rescue medication and/or rescue procedure uses will be set to missing; all missing data will then be imputed in the FAS using multiple imputation. In the main analyses of all binary responder-type endpoints, all subjects with missing data, regardless of reason for missingness, will be considered as nonresponders. In the main analysis of continuous or score endpoints, subjects with missing data will be handled using observed cases only, multiple imputation, or a linear mixed effect model.

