17.1.2. MISSING DATA METHODS FOR PRIMARY EFFICACY VARIABLE

Subjects who 1) discontinue the study for worsening of disease, lack of efficacy, or adverse event related to EoE, 2) use a rescue medication for EoE, or 3) have rescue medical procedure during the study as confirmed after blinded review by clinical and medical team members before study unblinding will be considered to have a missing outcome in the analysis of all efficacy endpoints at any subsequent timepoints, including the primary endpoint. The rescue medications/rescue medical procedure will be identified by the Pfizer clinical team during blinded data review. The detailed information regarding the identification of rescue therapy is provided in Appendix 4. In scenarios 2 and 3 above, if a subject has an efficacy measurement collected after the initiation of rescue medication/rescue medical procedure, the observed data will be censored at the time of initiation and they will be considered as having a missing outcome. Subjects in all 3 scenarios above may still be included in the respective Per Protocol Set, provided they do not violate other criteria for Per Protocol Set. For example, they will be excluded from the respective Per Protocol Set if they initiate a prohibited medication before the Week 16 efficacy assessment that can affect efficacy of the study treatment and the indication is unrelated to EoE.

Analysis visits will be mapped as per Section 6.4 before any missing data imputation method is applied.

Subjects who initiate rescue medication will have PEC results after the start of rescue medication/rescue medical procedure set to missing. All missing PEC at Week 16 and Week 24 will then be imputed using multiple imputation under missing at random (MAR) procedure with a fully conditional specification (FCS) and predictive mean

matching for PEC as the primary missing data method. There are two different types of missing data patterns: non-monotone and monotone. A subject with missing data at any post-Baseline visit, and a non-missing data point after that visit is said to have intermittent missing data (non-monotone). A subject with missing data at any post-Baseline visit and at all subsequent visits is said to have monotone missing data.

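### Rescue censoring in the SAP has no end date, so subjects rescued in Weeks 16 to 24 and then admitted to the extension may have their etrasimod results discarded or counted as nonresponse

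*SAP*

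**What the plan says.** **The censoring rule.** SAP 17.1.2 lists study discontinuation for worsening, lack of efficacy or an EoE-related adverse event, rescue medication, and rescue procedure. A subject with any of these "will be considered to have a missing outcome in the analysis of all efficacy endpoints at any subsequent timepoints". The SAP states in its Introduction that it "will cover the whole study period (i.e., Double-Blind Treatment Period and Extension Treatment Period".

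**Related rules.** For rescue after Week 16, key secondary estimand 3 in SAP 2.4 (reused for estimand 4) says that "any assessment after the rescue medication and/or rescue procedure time will be set to missing", again without a stop. SAP 17.2.2 makes rescue users nonresponders for the proportion endpoints and sets no time limit in that sentence. The protocol synopsis treats rescued subjects as failures at later timepoints. In SAP 8.3, for the main analyses of binary endpoints, "all subjects with missing data, regardless of reason for missingness, will be considered as nonresponders".

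**Who may enter the extension.** Protocol 4.3 admits completers of the Week 24 visit, "including subjects who discontinued study treatment due to lack of clinical efficacy and started rescue therapy between Weeks 16 and 24". It adds: "Rescue therapy must be discontinued on the day etrasimod is initiated in the Extension Treatment Period". Protocol 6.7.4 says the same in substance.

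**What the extension reports.** Biopsies are scheduled at Weeks 32 and 52 (Protocol Table 8). Protocol 11.5 plans descriptive summaries by four treatment sequences, including response outcomes and change from both the double-blind and the extension Baseline.

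**The concern.** The protocol deliberately keeps these subjects and gives them up to 28 weeks of etrasimod after rescue has stopped. The censoring rule was evidently written with Weeks 16 and 24 in mind, yet its wording runs to the end of the study. A programmer who follows it literally would discard biopsies and diary scores collected on etrasimod because of rescue taken before the extension began.

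Protocol 3.2 gives the extension two purposes: to describe durability, and to offer etrasimod to placebo subjects. Subjects who needed rescue on placebo and were then switched are among the most informative for the second. The placebo-to-etrasimod sequences are also the smallest groups, so a few subjects matter there.

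**Working it through.** The sample-size section is redacted and the point rests on no stated figure, so there is nothing to reproduce. The check compares texts, then sizes the result.

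**1. Follow one subject through the rules.** Take a placebo subject who stops study drug at Week 18 for lack of efficacy, takes rescue to Week 24, enters the extension and receives etrasimod.
- *Continuous endpoints.* SAP 17.1.2 makes every later value missing. Imputation of the peak eosinophil count (PEC) is specified for Weeks 16 and 24 only, so Week 32 and Week 52 values have no replacement and leave the summaries.
- *Binary endpoints.* SAP 8.3 and the protocol synopsis point to nonresponse. Protocol 11.4.1 frames its nonresponder rule for Weeks 16 and 24. The Efficacy Evaluable Set (SAP 5.10) is endpoint-specific and requires an extension measurement, so the subject might leave the denominator instead. The text does not settle which.
- *Is it rescue at all?* SAP Appendix 4 does not count rescue begun on or after the last study treatment dose. If that means the last double-blind dose, this subject's rescue is not rescue and the on-rescue Week 24 biopsy stands as observed. If it means the last dose in the study, 17.1.2 applies with no end.

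**2. Extension Baseline.** Protocol 11.3: "Baseline for the Extension Treatment Period is defined as the last measurement prior to the first etrasimod dose started at Week 24". For this subject that is a Week 24 biopsy taken on rescue. SAP 6.2 uses the last non-missing value. If censoring makes the Week 24 value missing, PEC Baseline falls back to Week 16. SAP 3.3 declares no changes from the protocol.

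**3. Size under nonresponder scoring.**
- Planned N = 96, allocated 3:3:2 (Protocol synopsis): placebo 96 × 2/8 = 24; each active arm 96 × 3/8 = 36.
- Placebo subjects re-randomized 1:1: 24/2 = 12 per sequence at most, if all enter.
- Let r be the share of a sequence rescued in Weeks 16 to 24, and p the true extension response rate, taken as equal in rescued and other subjects. The documents give neither; both are assumptions.
- Reported rate = p × (1 − r), so the drop is p × r.

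| r | Affected of 12 | Affected of 36 | Rate if p = 30% | Drop | Rate if p = 50% | Drop |
|---|---|---|---|---|---|---|
| 5% | 0.6 | 1.8 | 28.5% | 1.5 points | 47.5% | 2.5 points |
| 10% | 1.2 | 3.6 | 27.0% | 3 points | 45.0% | 5 points |
| 20% | 2.4 | 7.2 | 24.0% | 6 points | 40.0% | 10 points |

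One subject is 1/12 = 8.3 points of a placebo sequence, but is lost wrongly only if that subject truly responds. If censoring ended at the first extension dose, each rate would return to p.

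**The case against.** **A conflict inside the estimand table?** A reader might infer that the estimand table contradicts 17.1.2 for these subjects, because the primary estimand says that PEC "will have subsequent PEC data set to missing from that point forward through Week 24". That does not hold. As regards rescue, the sentence is written for rescue before the Week 16 assessment. For rescue after Week 16, estimands 3 and 4 have no Week 24 stop and agree with 17.1.2. The gap is the missing end date, not a contest between two rules.

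**Scored as failures?** This is a possible reading, not an established outcome. Protocol 11.4.1 and the Efficacy Evaluable Set point the other way, and 17.1.2 is headed for the primary variable, a Week 16 endpoint. Against that, its own sentence covers all efficacy endpoints. SAP text after 17.2.3.2 is redacted, and SAP 8.3 cites a section 16.3.2 that cannot be read. An extension rule could be there.

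**A larger bias?** A figure of 8 to 25 points (1/12 to 3/12) is tempting, but it needs every rescued switcher to be a true responder. It is an upper bound for one to three such subjects. If they leave the denominator instead, the p × r formula does not apply at all.

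**A baseline that makes etrasimod appear to raise PEC?** Protocol 11.5 already plans change from the double-blind Baseline, which for PEC comes from the Screening endoscopy, before any on-study rescue. The on-rescue Baseline distorts at most one of two planned summaries, and may not do so.

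**Consequence.** The extension is descriptive, with no between-group tests. This objection stands and limits the weight of the point.

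**Conclusion.** The point holds as a gap in the wording. The readable rules censor efficacy data after rescue without an end date, the protocol admits subjects rescued in Weeks 16 to 24 to the extension, and no readable passage restarts their data. Taken literally, their continuous extension results are lost and their binary results may be scored as nonresponse. Appendix 4 leaves it unclear whether their therapy counts as rescue.

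The effect is limited to descriptive extension summaries. Under nonresponder scoring it is about 1.5 to 10 points, resting on assumed r of 5 to 20% and p of 30 to 50%. The 12 per placebo sequence also assumes that all 24 placebo subjects enter. The documents do not support a claim that Week 16 results change: rescue begun after the Week 16 assessment leaves an observed Week 16 value intact.

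**What to change.** - In SAP 17.1.2, 17.2.2 and key secondary estimands 3 and 4, state that censoring for double-blind rescue ends at the first extension dose, and that extension data count from then until any new rescue in the extension. The Week 24 biopsy precedes that dose and stays censored.
- Limit the nonresponder rules in SAP 8.3 and the protocol synopsis, as they apply to double-blind rescue, to timepoints through Week 24.
- In Appendix 4, say whether the last study treatment means the last double-blind dose or the last dose in the study for subjects who restart.
- Reconcile Protocol 11.3 with SAP 6.2 on whether an on-rescue Week 24 value can serve as extension Baseline. For these subjects, rely on the already planned change from double-blind Baseline.
- Show extension results by sequence with and without subjects rescued in Weeks 16 to 24.

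The cost is wording and one extra descriptive table. It needs no new data and no change to treatment or rescue. The drawback is possible carry-over of the rescue effect at Week 32, eight weeks after rescue stops (32 − 24); the display with and without these subjects would help show it.

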5.5. PER PROTOCOL SET

The Per Protocol Set will consist of all subjects in the FAS without major protocol violations on or before Week 16 that might affect the evaluation of the effect of study treatment on the primary endpoint. This set will be used in sensitivity analyses of the primary and secondary endpoints to evaluate the influences of major protocol violators and deviators on the primary results. Subjects will be excluded from the Per Protocol Set if they violate the eligibility criteria or significantly deviate from the study plan, including:

- Study treatment non-compliance (< 80 or > 120%)
- Received incorrect study treatment for > 7 days in total
- Used rescue medication or undergo rescue medical procedure that may affect primary efficacy endpoint at Week 16
- Missed Week 16 esophageal PEC in pre-specified analysis window per Section 6.4 for reasons other than discontinuing due to lack of efficacy

All protocol deviations will be reviewed in addition to the programmable deviations listed above (e.g., study treatment non-compliance) to determine if any deviation is significant enough to exclude a subject from the Per Protocol Set. All exclusion flags will be finalized before study unblinding. Subjects excluded from the Per Protocol Set will be listed along with the reason category above. Subjects will be summarized by treatment to which they were randomized, regardless of treatment actually received.

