16.1. DERIVATIONS

Compliance to study treatment is based on the Drug Accountability eCRF and will be calculated as the number of tablets taken (total dispensed – total returned) divided by the prescribed number of tablets expected during the treatment period, expressed as a percentage, see calculations below.

The total number of tablets expected is defined as the number of tablets that a subject is expected to have taken between their first and last study treatment administration and is numerically identical to the subject's overall study treatment exposure, since the medication is to be taken once daily. On any site visit day, the medication is to be held and taken at the site, after all predose assessments have been completed. For example, if a subject took their last dose of study treatment on Day 60 and returned to the site on Day 78 to return the study treatment bottle, then the total number of tablets expected would be 60, not 77.

- Overall Compliance to study treatment will be calculated as follows:

$$\frac{([\text{Total N of tablets dispensed in the study}] - [\text{Total N of tablets returned in the study}])}{[\text{Date of last dose}] - [\text{Date of first dose}] + 1} \times 100$$

If a bottle is not returned, all dispensed tablets will be assumed to be taken. For each subject, if a high percentage (> 25%) of bottles were not returned by a subject, additional analyses may be done where bottles not returned are excluded from the overall compliance calculation for the subject. In such analysis, the date of last dose or the date of last bottle return, whichever is earlier, will be used as the “date of last dose” in the calculation above.

Both scheduled and unscheduled study treatment dispensations will be used in the compliance calculation. Overall

compliance calculations will be performed for the Double-Blind Treatment Period and the entire study and will be used in determining inclusion/exclusion of subjects in the Per Protocol Set. For subjects discontinued prior to Week 16, their overall compliance for the 16 Week Treatment Period and the entire study will be identical. For subjects who remained in the study beyond Week 16, the 16 Week total tablets expected will be defined as Date of Week 16 visit – Date of first dose, since their last dose in the 16 Week Treatment Period should have been taken on the day before Week 16 visit.

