APPENDIX 4. IDENTIFICATION OF RESCUE THERAPY

This appendix outlines the process the Pfizer clinical team/medical reviewers will use to determine rescue therapy for EoE in the APD334-206 study.

The objective of rescue therapy identification is to establish 1) intercurrent events for the efficacy estimands, and 2) exclusion of subjects from the Per Protocol Set(s).

Per protocol, rescue therapy is defined as any new therapy (ie, medication or procedure) or change in existing EoE therapy used to treat new or worsened EoE symptoms. In addition, use of certain medications/procedures that do not meet the definition of rescue therapy but are deemed to have significant impact on the efficacy assessment will be reviewed and may be considered as rescue therapy.

Only therapies reported on the electronic case report forms (eCRFs) will be assessed for rescue therapy determination. Use of rescue therapy during the follow-up period (beginning on or after the date of last study treatment administration) will not be considered as a rescue therapy.

The list of all rescue therapy uses in the study will be identified and finalized prior to study unblinding.

Medical procedure

- Esophagogastroduodenoscopy (EGD)
 - o Rule:
 - When dilation was done during EGD, any after first dose
 - When dilation was not done during EGD, any EGD with food bolus removal after first dose

Medications

- Proton Pump Inhibitors
 - o Examples of Medications
 - Omeprazole (Prilosec)
 - Lansoprazole (Prevacid)
 - Dexlansoprazole (Dexilant)
 - Esomeprazole (Nexium)
 - Pantoprazole (Protonix)
 - Rabeprazole (Aciphex)
 - o Rules
 - When used for EoE: any new initiation or change in dose after Day 1
 - When used for other disease (eg, GERD): New initiation or change in dose after Day 1 AND
 - Use > 4 weeks at the time of EGD OR
 - Use > 8 weeks with the end of treatment date falling within 4 weeks of EGD
- Corticosteroids
 - o Applicable route of administration: swallowed, oral, IM, SC, IV
 - o Examples of Medications
 - Fluticasone (Flovent)
 - Budesonide (Pulmicort, Flexhaler)
 - Betamethasone
 - Cortisone
 - Deflazacort
 - Dexamethasone
 - Fludrocortisone
 - Hydrocortisone
 - Methylprednisolone
 - Prednisone
 - Prednisolone

- Triamcinolone
- Rules
 - When used for EoE: any new initiation after Day 1
 - When used for other diseases: any new initiation after Day 1 AND
 - Use > 7 days at the time of EGD OR
 - Use > 14 days with the end of treatment date falling within 8 weeks of EGD

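### Per Protocol Set rules conflict for EoE rescue begun before the Week 16 endoscopy, and no compliance window is named as the one that decides membership

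*SAP*

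**What the plan says.** **Rescue.** SAP 5.5 lists among the reasons for exclusion from the Per Protocol Set: "Used rescue medication or undergo rescue medical procedure that may affect primary efficacy endpoint at Week 16". SAP Appendix 4 gives two objectives for identifying rescue therapy, and the second is exclusion from the Per Protocol Set. SAP 17.1.2 describes three scenarios: leaving the study for worsening, lack of efficacy or an EoE-related adverse event; using rescue medication for EoE; and having a rescue procedure. It then says: "Subjects in all 3 scenarios above may still be included in the respective Per Protocol Set, provided they do not violate other criteria". Its one example of exclusion is a subject who would "initiate a prohibited medication before the Week 16 efficacy assessment that can affect efficacy of the study treatment and the indication is unrelated to EoE".

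**Discontinuation.** SAP 5.5 also excludes a subject who "Missed Week 16 esophageal PEC in pre-specified analysis window per Section 6.4 for reasons other than discontinuing due to lack of efficacy". Lack of efficacy is the only exempt reason.

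**Compliance.** The set in SAP 5.5 holds subjects "without major protocol violations on or before Week 16", with a compliance limit of 80% to 120% but no window attached to that limit. SAP 16.1 says that overall "compliance calculations will be performed for the Double-Blind Treatment Period and the entire study and will be used in determining inclusion/exclusion of subjects" in this set. The same paragraph defines a 16-week tablet denominator but does not say that it decides membership.

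Protocol Table 6 leaves the final definition of the set to the SAP, so it settles none of this.

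**The concern.** The Per Protocol analysis is a planned check on the primary endpoint and all four key secondary endpoints (SAP 17.2.1, table of planned analyses). Its stated purpose is to show how far protocol violators influence the result. If one section removes a subject and another keeps that subject, the check has no single definition.

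The two rescue rules also answer different questions. Under one, rescued subjects leave the denominator. Under the other, they stay without an observed Week 16 value, because 17.1.2 sets data after rescue to missing.

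The compliance rule raises a separate problem. A set meant to describe adherence up to the Week 16 endpoint can be decided by tablets taken after it. It can therefore drop subjects who adhered when it mattered and keep subjects who did not.

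**Working it through.** **Rescue and discontinuation: the rules side by side**

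| Subject | SAP 5.5 and Appendix 4 | SAP 17.1.2 | Result |
|---|---|---|---|
| EoE rescue started before the Week 16 EGD, able to affect the endpoint | Excluded | May stay | Conflict |
| EoE rescue only after the Week 16 EGD | Not excluded on this ground | May stay | Agree |
| Leaves for lack of efficacy, Week 16 PEC missed | Exempt | May stay | Agree |
| Leaves for worsening or EoE-related adverse event, Week 16 PEC missed | Excluded | May stay | Conflict, subject to the proviso discussed under the objection |

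**Compliance: reproducing the SAP's example.** Tablets expected = last dose day − first dose day + 1. With last dose on Day 60, 60 − 1 + 1 = 60, as SAP 16.1 states. The rejected figure is 78 − 1 = 77.

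**Tablets expected per window, visits on schedule**
- 16 weeks (Week 16 visit date − first dose date): 113 − 1 = 112. The 80% limit is 89.6, so fewer than 90 tablets fails.
- Double-blind period: 168, of which 168 − 112 = 56 fall after Week 16. The limit is 134.4.
- Entire study: 364 or 365, depending on whether the Week 52 visit-day dose counts, of which 252 or 253 fall after Week 16. The limit is 291.2 or 292.

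**The same subject under each window**

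| Pattern | 16 weeks | Double-blind | Entire study (364) |
|---|---|---|---|
| 100% to Week 16, then 50% | 112/112 = 100%, in | (112 + 28)/168 = 83%, in | (112 + 126)/364 = 65%, out |
| 60% to Week 16 (67/112), then 100% | 60%, out | (67 + 56)/168 = 73%, out | (67 + 252)/364 = 88%, in |

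Using 365 tablets gives 65% and 88% again.

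**Lowest Week 16 compliance that still passes with perfect dosing afterwards**
- Double-blind: (79 + 56)/168 = 80.4%, so 79/112 = 70.5% by Week 16 is enough.
- Entire study: (40 + 252)/364 = 80.2% or (39 + 253)/365 = 80.0%, so 40/112 or 39/112, about 35%, is enough.

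**Later missed tablets that remove a subject fully compliant to Week 16**
- Double-blind: 34 of 56 (61%).
- Entire study: 73 of 252 or 74 of 253 (29%).

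**Timing.** SAP 4.1 places the Main Analysis after Week 24, and SAP 5 and 5.1 require the sets to be approved before that unblinding. Entire-study compliance is then unfinished for anyone still in the extension. Recomputing it for the Final Analysis could change membership after sponsor staff know the double-blind assignments.

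**What the rescue choice changes**
- *Percent change in PEC:* SAP 17.1.5 repeats the primary model in the Per Protocol Set. The imputation in 17.1.3 is fitted separately by arm, so a retained rescue user would receive an imputed value. This rests on 17.1.5; the footnote on the Per Protocol cell says only that values after rescue are set to missing.
- *PEC < 15 and ≤ 6:* the footnote counts missing data as nonresponse, so a retained rescue user is a failure.

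**Possible numbers (assumption).** The documents give no rescue rate. The planned arms are 96 × 3/8 = 36, 36 and 96 × 2/8 = 24. If 5% to 15% started EoE rescue before the Week 16 EGD, that is 1.8 to 5.4 subjects per etrasimod arm and 1.2 to 3.6 on placebo. These are ceilings, since some would fail another criterion under either reading. To illustrate, again by assumption, 12 responders of 36 is 33%; with five rescued nonresponders removed, 12 of 31 is 39%.

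**The case against.** SAP 5.5 does not exclude all rescue. It requires a possible effect on the Week 16 endpoint, settled at blinded review. The scenarios in 17.1.2 run through the whole study, and Protocol 6.7.4 expressly offers subjects who stop between Weeks 16 and 24 the option to remain on rescue. For them, keeping the subject fits 5.5. A reader might infer that the two sections contradict each other for every rescue user; the documents do not support that. What remains is EoE rescue before the Week 16 EGD. The proviso does not remove it, because the other criteria are those beyond the three scenarios, and the example ties exclusion to a non-EoE indication. For discontinuation the proviso has more force: a missed Week 16 PEC can be read as another criterion. The wording still invites two answers.

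On compliance, the natural reading is the 16-week window, given the time limit in 5.5 and the denominator defined in 16.1. That is a fair guess at intent, but 16.1 assigns the decision to the two longer windows. A reader might go further and infer that membership is mostly determined after the endpoint. The share (52 − 16)/52 = 69% holds only if the entire-study window governs. For the double-blind window it is (24 − 16)/24 = 33%.

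A reader might also infer that retained rescue users are imputed for every endpoint, or that the main result is in doubt. Neither follows. The responder endpoints count them as failures. The primary and secondary analyses use the Full Analysis Set, and this Phase 2 trial makes no claim of type I error control.

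**Conclusion.** The inconsistency is real and narrow. It covers EoE rescue begun before the Week 16 EGD, the reasons that excuse a missed Week 16 PEC, and the compliance window. The window matters most in arithmetic terms. As written, the entire-study rule can exclude a subject with perfect adherence to Week 16 and include one with about 35%, and it cannot be completed for subjects still in the extension when sets are approved for the Main Analysis. Those figures assume on-schedule visits and the later dosing patterns shown. The number of subjects affected by the rescue conflict cannot be derived from the documents. Only the supplementary and sensitivity analyses in the Per Protocol Set are affected; no primary estimate or p-value changes. It should be corrected because the set exists to test the main result and its membership ought not to depend on which section is followed.

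**What to change.** Before unblinding for the Main Analysis:

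- **SAP 16.1:** state that only compliance from first dose to Week 16, using the denominator already defined there, decides Per Protocol membership. Keep the double-blind and entire-study figures as descriptive summaries.
- **SAP 17.1.2:** correct the sentence so that subjects whose rescue started before the Week 16 EGD and may affect the Week 16 endpoint are excluded, as 5.5 states and Appendix 4 intends. Say that subjects rescued only after that EGD may stay if they meet the other criteria.
- **SAP 17.1.2 and 5.5:** make the exempt reasons for discontinuation the same, following 5.5.

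This is an analysis-set rule only and does not touch when rescue may be given. The cost is a few sentences of SAP text, with no new data and no change to conduct or sample size.
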